7. RESEARCH QUESTION AND OBJECTIVES

What is the prevalence of rare blood cancers in Europe?

Study objectives

Objective 1: To estimate the prevalence of follicular lymphoma between 1st January 2010 and the end of available data in data sources from across Europe, stratified by age and sex

Objective 2: To estimate the prevalence of diffuse Large B-Cell Lymphoma between 1st January 2010 and the end of available data in data sources from across Europe, stratified by age and sex

Objective 3: To estimate the prevalence of multiple myeloma between 1st January 2010 and the end of available data in data sources from across Europe, stratified by age and sex

Objective 4: To estimate the prevalence of chronic lymphocytic leukaemia between 1st January 2010 and the end of available data in data sources from across Europe, stratified by age and sex

Objective 5: To estimate the prevalence of acute myeloid leukaemia between 1st January 2010 and the end of available data in data sources from across Europe, stratified by age and sex

Objective 6: To estimate the prevalence of acute lymphocytic leukaemia between 1st January 2010 and the end of available data in data sources from across Europe, stratified by age and sex

Table 1. Primary research questions and objectives

Objective:	To estimate the prevalence of rare blood cancers (follicular lymphoma, diffuse Large B-Cell Lymphoma, Multiple Myeloma, Chronic Lymphocytic Leukaemia, Acute Myeloid Leukaemia, Acute Lymphocytic Leukaemia)
Hypothesis:	Not applicable
Population (mention key inclusion-exclusion criteria):	All persons in the selected databases will be eligible for inclusion in the study (for main analysis all patients need to have at least 1 year of database history)
Exposure:	Not applicable
Comparator:	Not applicable
Outcome:	Rare blood cancers: Follicular lymphoma, Diffuse Large B-Cell Lymphoma, Multiple Myeloma, Chronic Lymphocytic Leukaemia, Acute Myeloid Leukaemia, Acute Lymphocytic Leukaemia
Time (when follow up begins and ends):	1 st January 2010 – end of available data within data sources
Setting:	5 Electronic Health Care Record databases across Europe
Main measure of effect:	Prevalence

	D2.2.3 – Study Protocol for C1-001	
	Author(s): [name], [name], [name], [name]	Version: 2.0 - Final
		Dissemination level: Public

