IQVIA LPD Belgium is a computerised network of GPs who contribute to a centralised database of anonymised data of patients with ambulatory visits. Currently, around 300 GPs from 234 practices are contributing to the database covering 1.1M patients from a total of 11.5M Belgians (10.0%). The database covers time from 2005 through the present. Observation time is defined by the first and last consultation dates.

	D2.2.3 – Study Protocol for C1-001	
	Author(s): [name], [name], [name], [name]	Version: 2.0 - Final
	Dissemination level: Public	

IQVIA Disease Analyser (DA) Germany

IQVIA Disease Analyser (DA) Germany is collected from extracts of patient management software used by GPs and specialists practicing in ambulatory care settings. Data coverage includes more than 34M distinct person records out of a total population of 80M (42.5%) in the country and collected from 2,734 providers. Patient visiting more than one provider are not cross identified for data protection reasons and therefore recorded as separate in the system. Dates of service include from 1992 through present. Observation time is defined by the first and last consultation dates. Germany has no mandatory GP system and patients have free choice of specialist. As a result, data are collected from visits to 28.8% General, 13.4% Orthopaedic Surgery, 11.8% Otolaryngology, 11.2% Dermatology, 7.7% Obstetrics/Gynaecology, 6.2% various Neurology and Psychiatry 7.0% Paediatric, 4.6% Urology, 3.7% Cardiology, 3.5% Gastroenterology, 1.5% Pulmonary and 0.7% Rheumatology practices.

Table 2. Description of the selected Data Sources.

Country	Name of Database	Justification for Inclusion	Health Care setting (e.g. primary care, specialist care, hospital care)	Type of Data (EHR, claims, registries)	Number of active subjects
The Netherlands	Integrated Primary Care Information Project (IPCI)	Database selected for Y1 of Darwin EU® and has information on blood cancers	Primary care	EHR	1.4 million
Spain	Sistema d'Informació per al Desenvolupament de la Investigació en Atenció Primària (SIDIAP)	Database selected for Y1 of Darwin EU® and has information on blood cancers	Primary care with hospital linkage	EHR	5.8 million
United Kingdom	The Clinical Practice Research Datalink (CPRD) GOLD database	Database selected for Y1 of Darwin EU® and has information on blood cancers	Primary care	EHR	3 million

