8.5 Study Population with inclusion and exclusion criteria

All persons in a database will be eligible for inclusion in the study. They will though only enter the study if they have some observation time during the study period. For the primary analysis, study participants will be required to have a year of prior history observed before contributing observation time. This is to ensure a minimum prior observation time to identify any ongoing outcomes (i.e. rare blood cancer) at the time at which a participant enters the study. In sensitivity analyses the requirement for prior history will first be removed, and then increased to three years.

Table 3. Operational Definitions of Inclusion Criteria

Criterion	Details	Order of application*	Assessment window	Care Settings	Code Type	Diagnosis position	Applied to study populations:	Measurement characteristics/ validation	Source for algorithm
Prior database history	Study participants will be	After	1 year	Primary care and combination of	N/A	N/A	All individuals within the	N/A	N/A

	D2.2.3 – Study Protocol for C1-001	
	Author(s): [name], [name], [name], [name]	Version: 2.0 - Final
	Dissemination level: Public	

of 1 year	required to have a year of prior history observed before contributing observation time			primary and secondary care for IQVIA Germany			selected databases		
-----------	--	--	--	--	--	--	--------------------	--	--

* After as first possible study entry date is selected and then it is checked whether patient has one year of database history. In a sensitivity analysis, this rule will be removed. In another sensitivity analysis, required history will be increased to 3 years. N/A: not applicable for this study or data sources being used

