Follicular lymphoma	For clinical description of outcome, see above	Yes	Binary	N/A	Primary care and combination of primary and secondary care for IQVIA Germany	SNOMED	N/A	All individuals within the selected databases	N/A	N/A
Diffuse Large B-Cell Lymphoma	For clinical description of outcome, see above	Yes	Binary	N/A	Primary care and combination of primary and secondary care for IQVIA Germany	SNOMED	N/A	All individuals within the selected databases	N/A	N/A
Multiple myeloma	For clinical description of outcome, see above	Yes	Binary	N/A	Primary care and combination of primary and secondary care for IQVIA Germany	SNOMED	N/A	All individuals within the selected databases	N/A	N/A
Chronic lymphoc	For clinical	Yes	Binary	N/A	Primary care and	SNOMED	N/A	All individuals	N/A	N/A

	D2.2.3 – Study Protocol for C1-001	
	Author(s): [name], [name], [name], [name]	Version: 2.0 - Final
	Dissemination level: Public	

Outcome name	Details	Primary outcome?	Type of outcome	Wash out window	Care Settings ¹	Code Type ²	Diagnosis Position ³	Applied to study populations:	Measurement characteristics/ validation	Source of algorithm
lytic leukaemia	description of outcome, see above				combination of primary and secondary care for IQVIA Germany			all within the selected databases		
Acute myeloid leukaemia	For clinical description of outcome, see above	Yes	Binary	N/A	Primary care and combination of primary and secondary care for IQVIA Germany	SNOMED	N/A	All individuals within the selected databases	N/A	N/A
Acute lymphocytic leukaemia	For clinical description of outcome, see above	Yes	Binary	N/A	Primary care and combination of primary and secondary care for IQVIA Germany	SNOMED	N/A	All individuals within the selected databases	N/A	N/A

N/A: not applicable for this study or data sources being used

	D2.2.3 – Study Protocol for C1-001	
	Author(s): [name], [name], [name], [name]	Version: 2.0 - Final
		Dissemination level: Public

8.6.3. Other covariates, including confounders, effect modifiers and other variables (where relevant)

Two age groupings will be used: 1) 0-9; 10-19; 20-29; 30-39; 40-49; 50-59; 60-69; 70-79; 80-89; 90-99; 100+, and 2) 0-44; 45-64; 65 and over. The latter, broader, age groups will be used where low counts preclude reporting results for the 10-year age bands. The sex (male/ female) of study participants will also be identified.

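### IQVIA DA Germany counts person-provider records from all specialties, so the German prevalence is not per individual and is likely, though not certainly, too low against 5 in 10,000

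*Protocol*

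**What the plan says.** Protocol section 8.2 describes IQVIA DA Germany as drawn from the practice software of GPs and ambulatory specialists. On coverage it states: "Data coverage includes more than 34M distinct person records out of a total population of 80M (42.5%) in the country". It then says: "Patient visiting more than one provider are not cross identified for data protection reasons and therefore recorded as separate in the system". The specialty mix is given as "As a result, data are collected from visits to 28.8% General, 13.4% Orthopaedic Surgery, 11.8% Otolaryngology, 11.2% Dermatology", followed by "7.7% Obstetrics/Gynaecology, 6.2% various Neurology and Psychiatry 7.0% Paediatric, 4.6% Urology, 3.7% Cardiology, 3.5% Gastroenterology, 1.5% Pulmonary and 0.7% Rheumatology practices".

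The population rule is the same for every source. Section 8.5 has "All persons in a database will be eligible for inclusion in the study", Table 1 in section 7 repeats it, and Table 4 in section 8.6.2 applies each outcome to "All individuals within the selected databases". Tables 3 and 4 label the German care setting as primary and secondary care combined. No section restricts Germany by specialty or describes any removal of duplicates.

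The list of abbreviations and section 8.8 both define prevalence as a number of individuals with the outcome over the population at risk. Section 6 gives the orphan threshold as at most 5 in 10,000, and the abstract says the aim is to see whether these cancers still qualify as rare.

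**The concern.** A person who sees a GP, an orthopaedic surgeon and a dermatologist, all contributing to the database, appears as three persons in the denominator. The blood cancer code may sit in only one of the three records. Most of the listed mix is non-GP, and the specialties most likely to manage these cancers are not listed. The unit of analysis is thus a person at a provider, and cases are probably coded in fewer of their records than the denominator assumes.

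Germany is the largest source in Table 2, with 8.5 million active subjects. A downward bias there favours concluding that a cancer is still rare. Every row of Table 5 uses the same all-specialty German population. Section 11 does not mention duplicate persons or specialty mix, and the checklist in Appendix II marks selection bias, information bias and control of outcome misclassification as not applicable.

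**Working it through.** **Inputs from the Protocol.** Specialty shares, 34 million records and a population of 80 million (section 8.2); 8.5 million active subjects (Table 2); threshold 5 per 10,000 (section 6). **Assumed, not in the Protocol:** k, the rate at which a non-GP record carries the cancer code relative to a GP record, shown from 0 to 1; and that the listed shares equal shares of the analysed records.

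**1. The plan's own coverage figure.** 34 / 80 = 0.425, so 42.5% reproduces. The numerator counts records that are separate for each provider and the denominator counts people, so the ratio is not population coverage.

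**2. Specialty mix.** 28.8 + 13.4 + 11.8 + 11.2 = 65.2. The remaining items are 7.7 + 6.2 + 7.0 + 4.6 + 3.7 + 3.5 + 1.5 + 0.7 = 34.9. The total is 100.1%, which is rounding, so there is no room for an unlisted haematology or oncology share. Non-GP is 100 - 28.8 = 71.2%.

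**3. Effect of specialty mix (illustration).** Factor = 0.288 + 0.712k.

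| k | Factor | GP-record prevalence of 5.0 per 10,000 reads as | GP-record prevalence that would read as 5.0 |
|---|---|---|---|
| 0 | 0.288 | 1.44 | 17.4 |
| 0.25 | 0.466 | 2.33 | 10.7 |
| 0.5 | 0.644 | 3.22 | 7.8 |
| 1 | 1.000 | 5.00 | 5.0 |

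**4. Effect of duplication alone.** Observed prevalence = true prevalence × (coded records per case) / (records per person). For a true 5.0 per 10,000:
- 2 coded records per case and 2 records per person: 5.0, no bias.
- 1 coded and 2 records per person: 2.5.
- 1 coded and 3 records per person: 1.67.
- 2 coded and 1.5 records per person: 6.67, an upward bias.

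Duplication therefore biases downwards only if cases have fewer coded records than people on average have records.

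**5. Precision under a general-plus-paediatric restriction.** Share = 28.8 + 7.0 = 35.8%. Records = 8.5 million × 0.358 = 3.04 million. Cases at 5 per 10,000 = about 1,520. Relative 95% half-width = 1.96 / √1,520 = 5.0%. For all 8.5 million: 4,250 cases and 1.96 / √4,250 = 3.0%. Both apply the listed shares to active subjects and are approximate.

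**6. What Table 5 varies.** Its 27 rows (number 6 appears twice) change the prevalence type, point or period estimate, prior history and observable time. None changes specialty.

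**The case against.** The strongest case against concerns size and certainty. A reader might infer from the 28.8% that the German figure is cut to about 0.29 of the truth. The Protocol does not support that, for four reasons.

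- No recording rate by specialty is given, so k is unknown. The code lists in Appendix I include cutaneous, gastric, intestinal, testicular, prostatic and cervical lymphomas, so dermatology, gastroenterology, urology and gynaecology practices can plausibly record some cases. Zero is an extreme value of k.
- The listed percentages may be shares of visits or of practices, and neither is the share of the analysed denominator. German observation time runs from first to last consultation, and the primary analysis requires 365 days of history. Short specialist episodes drop out, and the remaining mix is not stated.
- Duplication is neutral if all of a case's records carry the code. Cases counted twice, and the advantage that consultation-based observation gives to frequent attenders, could offset the bias in part.
- A reader might also infer that the German analysis should be confined to GPs. That would drop the 7.0% paediatric practices in a country that section 8.2 describes as having no mandatory GP system, while Appendix I calls ALL the most frequent childhood neoplasm. Objective 6 and the 0-9 band would suffer most.

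It is also fair that section 8.2 discloses the non-linkage and the mix, that section 11 warns of false negatives and of variable recording between databases, and that section 8.9 keeps databases separate, so other countries' results are unaffected.

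All of this stands as a limit on magnitude and on the form of the repair. It does not remove the mismatch between the defined measure and the German unit of analysis. The history and observable-time variants in Table 5 may alter how many short specialist records enter, but they do not isolate specialty.

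**Conclusion.** The point holds as a mismatch of unit with a likely downward bias. As planned, the German result is a prevalence per person-provider record over all specialties, whereas the Protocol defines prevalence per individual and reads it against 5 in 10,000.

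The downward direction rests on non-GP records carrying these codes less often than GP records. That is plausible with no haematology or oncology listed, and it fits section 11's expectation that false negatives outnumber false positives, but it is not shown. The factors from 0.29 to 1.0 are illustrations that depend on an assumed k and on equating listed shares with record shares. They are not estimates of the bias. Neither a definite dilution nor a specific corrected prevalence can be claimed from the Protocol.

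**What to change.** - **Sections 8.2, 8.5 and Table 5:** add for IQVIA DA Germany an analysis with numerator and denominator both restricted to general plus paediatric practices. Paediatrics is needed for ALL and the youngest age bands. Report it beside the all-specialty result, and state that the all-specialty German figure will not be compared with 5 in 10,000 on its own.
- **Section 8.2:** restate the 42.5% as person-provider records relative to the population, not population coverage, and say whether the specialty percentages are shares of visits or of practices.
- **Section 11:** add duplicate records and specialty mix as limitations, with the likely direction and the possible offsets.

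The cost is one filter on provider specialty and an extra set of German results. Relative 95% intervals at the threshold widen from roughly ±3.0% to about ±5%, if the listed shares approximate record shares. Some duplication between practices remains, and cases coded only in haematology or oncology would still be missed.

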8.3 Study Period

The study period will be between 1st January 2010 and the end of available data in each of the data sources.

8.4 Follow-up

Study participants will begin contributing person time on the respective date of the latest of the following: 1) study start date (1st January 2010), 2) date at which they have sufficient prior history (365 days, or if there is no requirement for prior history this date will coincide with the date at which their observation period starts), 3) date at which they reach a minimum age (where age strata are being considered). Participants will stop contributing person time at the earliest date of the following: 1) study end date (end of available data in each of the data sources), 2) date at which their observation period ends, 3) the last day in which they have the maximum age (where age strata are being considered). Where there are multiple age strata, study participants will contribute to each strata while they satisfy the conditions of that strata (i.e. when they reach the limit of one age strata they will begin contributing to the next).

An overview of study entry and exit is shown below in **Figure 1** for the overall analysis, with entry of exit for a given age strata shown in **Figure 2**. In this latter example person ID 1 and 3 enter the study on the day they reach the minimum age and exits at the study end date. Person ID 2 enters the study on the study start date and exits at the maximum age. Person ID 4 enters the study on the day they reach the minimum age and leaves when they exit the database (the end of their observation period). Person ID 5 enters the study on the day they have sufficient prior history and exits at the study end date. Lastly, person ID 6 has two observation periods in the database. For the first they enter and contribute time until their exit, for the second they start contributing time again once they have sufficient prior history and exit at the maximum age.

	D2.2.3 – Study Protocol for C1-001	
	Author(s): [name], [name], [name], [name]	Version: 2.0 - Final
	Dissemination level: Public	

[figure not shown]

Figure 1 Included observation time for study participants overall

	D2.2.3 – Study Protocol for C1-001	
	Author(s): [name], [name], [name], [name]	Version: 2.0 - Final
	Dissemination level: Public	

[figure not shown]

Figure 2. Included observation time for study participants for a given age strata

8.5 Study Population with inclusion and exclusion criteria

All persons in a database will be eligible for inclusion in the study. They will though only enter the study if they have some observation time during the study period. For the primary analysis, study participants will be required to have a year of prior history observed before contributing observation time. This is to ensure a minimum prior observation time to identify any ongoing outcomes (i.e. rare blood cancer) at the time at which a participant enters the study. In sensitivity analyses the requirement for prior history will first be removed, and then increased to three years.

Table 3. Operational Definitions of Inclusion Criteria

Criterion	Details	Order of application*	Assessment window	Care Settings	Code Type	Diagnosis position	Applied to study populations:	Measurement characteristics/ validation	Source for algorithm
Prior database history	Study participants will be	After	1 year	Primary care and combination of	N/A	N/A	All individuals within the	N/A	N/A

	D2.2.3 – Study Protocol for C1-001	
	Author(s): [name], [name], [name], [name]	Version: 2.0 - Final
	Dissemination level: Public	

of 1 year	required to have a year of prior history observed before contributing observation time			primary and secondary care for IQVIA Germany			selected databases		
-----------	--	--	--	--	--	--	--------------------	--	--

* After as first possible study entry date is selected and then it is checked whether patient has one year of database history. In a sensitivity analysis, this rule will be removed. In another sensitivity analysis, required history will be increased to 3 years. N/A: not applicable for this study or data sources being used

8.6 Variables

8.6.1. Exposure/s (where relevant)

N/A as no specific drugs of interests are investigated.

8.6.2. Outcome/s (where relevant)

Outcome cohort definitions for partial and complete prevalence

Complete prevalence represents the number of persons alive at the specific point in time regardless of how long ago the diagnosis was, while partial prevalence limits the number of patients to those diagnosed during a fixed time in the past.⁶ To operationalise this definition outcome cohorts will be defined which vary in how the cohort exit is defined. For complete prevalence an individual will remain in the outcome cohort until the end of their observed time at risk. Meanwhile, for partial prevalence, an individual will exit the outcome cohort after a certain number of days has elapsed since the first record indicating them to be a prevalent case (e.g. 1,825 days for 5-year partial prevalence).

Follicular lymphoma

Follicular lymphomas are the second leading Non-Hodgkin’s lymphomas and can be diagnosed accurately on morphologic findings alone: B-cell in follicular centre. Many patients are diagnosed incidentally or at a time when their lymphoma is not causing symptoms or signs of organ function impairment. The major differential diagnosis is between lymphoma and reactive follicular hyperplasia. The coexistence of diffuse large B-cell lymphoma must be considered. Patients with follicular lymphomas are often subclassified, or graded, into those with predominantly small cells, those with a mixture of small and large cells, and those with predominantly large cells. The typical natural history is a pattern of continuous relapses with a diminishing sensitivity to chemotherapy. On average, most patients will live with follicular lymphoma for 15 to 20 years.

For this study, cases will be identified based on a record indicating a diagnosis or observation of follicular lymphoma. A clinical description along with a preliminary code list is provided in Appendix 1. For the primary analysis, 5-year partial prevalence will be estimated and so individuals will be considered as a prevalent case if they had a relevant record observed in the prior 1,825 days. In sensitivity analyses, 2-year partial prevalence

	D2.2.3 – Study Protocol for C1-001	
	Author(s): [name], [name], [name], [name]	Version: 2.0 - Final
		Dissemination level: Public

will be estimated (using records in the prior 730 days) as will complete prevalence. For the latter, individuals will continue to be considered as a prevalent case from their first observed diagnosis or observation of follicular lymphoma up until the end of their observation time.

Diffuse Large B-Cell Lymphoma

Diffuse Large B-Cell Lymphoma is the most common Non-Hodgkin lymphoma, accounting for about 1 in 3 of these conditions. Diffuse Large B-Cell Lymphoma is also more common in people with a family history and in the immuno-compromised (individuals on immune suppressive therapy or with a condition like HIV or EBV-related). It is common for diffuse Large B-Cell Lymphoma to be diagnosed at an advanced stage, with involvement of bone marrow, CNS, GI, thyroid, liver, and/or skin.

For this study, cases will be identified based on a record indicating a diagnosis or observation of large B-Cell lymphoma. A clinical description along with a preliminary code list is provided in Appendix 1. For the primary analysis, 5-year partial prevalence will be estimated and so individuals will be considered as a prevalent case if they had a relevant record observed in the prior 1,825 days. In sensitivity analyses, 2-year partial prevalence will be estimated (using records in the prior 730 days) as will complete prevalence. For the latter, individuals will continue to be considered as a prevalent case from their first observed diagnosis or observation of large B-Cell lymphoma up until the end of their observation time.

Multiple myeloma

Multiple myeloma is a malignant uncontrolled proliferation of plasma cells derived from one single clone. Multiple myeloma can affect many organs, typically bones and calcium metabolism, kidneys, immune system, blood, and more rarely neurologic. Diagnosis is typically obtained after bone marrow biopsy, where plasma cells, monoclonal kappa or lambda light chains will be present. The most important differential diagnosis is monoclonal gammopathy of unknown significance (MGUS) or 'smoldering multiple myeloma'.

For this study, cases will be identified based on a record indicating a diagnosis or observation of multiple myeloma. A clinical description along with a preliminary code list is provided in Appendix 1. For the primary analysis, 5-year partial prevalence will be estimated and so individuals will be considered as a prevalent case if they had a relevant record observed in the prior 1,825 days. In sensitivity analyses, 2-year partial prevalence will be estimated (using records in the prior 730 days) as will complete prevalence. For the latter, individuals will continue to be considered as a prevalent case from their first observed diagnosis or observation of multiple myeloma up until the end of their observation time.

Chronic lymphocytic leukaemia

Chronic lymphocytic leukaemia is a neoplasm characterised by the proliferation and accumulation of lymphocytes, usually B lineage, immune-incompetent. It is characterised by an invasion of peripheral and medullary blood by lymphocytes, and is of low aggressiveness. In most cases it presents asymptotically (incidental finding of lymphocytosis). The clinical manifestations of this disease are due to the progressive infiltration of the bone marrow, lymph nodes and other tissues by lymphocytes, and to immunological alterations. Chronic lymphocytic leukaemia is a very common entity, especially in elderly patients. Therefore, in the presence of lymphocytosis with conclusive flow cytometry in peripheral blood, the diagnosis is a fact and no further complementary studies will be required if the patient is asymptomatic and has no treatment criteria. Carrying out more complex diagnostic techniques such as bone marrow biopsy, mutation studies, cytogenetics or imaging tests are only justified if the patient is symptomatic or meets treatment criteria.

For this study, cases will be identified based on a record indicating a diagnosis or observation of chronic lymphocytic leukaemia. A clinical description along with a preliminary code list is provided in Appendix 1. For the primary analysis, 5-year partial prevalence will be estimated and so individuals will be considered as a

	D2.2.3 – Study Protocol for C1-001	
	Author(s): [name], [name], [name], [name]	Version: 2.0 - Final
		Dissemination level: Public

prevalent case if they had a relevant record observed in the prior 1,825 days. In sensitivity analyses, 2-year partial prevalence will be estimated (using records in the prior 730 days) as will complete prevalence. For the latter, individuals will continue to be considered as a prevalent case from their first observed diagnosis or observation of chronic lymphocytic leukaemia up until the end of their observation time.

Acute myeloid leukaemia

Acute myeloid leukemia is the most common acute leukemia in older patients. Characterised by the infiltration of blood, bone marrow and sometimes other tissues by proliferative, poorly differentiated hematopoietic cells. Mostly presenting with nonspecific symptoms that begin gradually, or abruptly, and are the consequence of anemia, leukocytosis, leukopenia/leukocyte dysfunction, or thrombocytopenia, typically up to 3 months before diagnosis. Long-term survival is infrequent, at about 1 in 4 in 5 years from diagnosis.

For this study, cases will be identified based on a record indicating a diagnosis or observation of acute myeloid leukaemia. A clinical description along with a preliminary code list is provided in Appendix 1. For the primary analysis, 5-year partial prevalence will be estimated and so individuals will be considered as a prevalent case if they had a relevant record observed in the prior 1,825 days. In sensitivity analyses, 2-year partial prevalence will be estimated (using records in the prior 730 days) as will complete prevalence. For the latter, individuals will continue to be considered as a prevalent case from their first observed diagnosis or observation of acute myeloid leukaemia up until the end of their observation time.

Acute lymphocytic leukaemia

Acute lymphocytic leukaemia is a type of cancer that affects white blood cells. In acute lymphocytic leukaemia, the process of development of blood cells is faulted, with immature, non-functioning leukemic cells being released from hematopoietic progenitors in the bone marrow or lymphatic system. This leads to anaemia, granulocytopenia, and thrombocytopenia, and causes symptoms of fatigue, weakness, breathlessness, infection, and haemorrhage. Common symptoms when patients first seek medical advice include fatigue and feeling breathless, repeated infections over a short time and unusual and frequent bleeding. Other symptoms can comprise pale, easily bruised skin; high temperature and night sweats; bone and joint pain as well as swollen lymph nodes, abdominal pain and unintentional weight loss. In some cases the central nervous system is also affected, with neurological symptoms including headaches, seizures, blurred vision or dizziness being reported. Acute lymphocytic leukaemia generally progresses quickly and aggressively, with immediate treatment being required. Prognosis is highly age-related, with cure rates of around 90% in children, decreasing to <10% in elderly or frail patients

For this study, cases will be identified based on a record indicating a diagnosis or observation of acute lymphocytic leukaemia. A clinical description along with a preliminary code list is provided in Appendix 1. For the primary analysis, 5-year partial prevalence will be estimated and so individuals will be considered as a prevalent case if they had a relevant record observed in the prior 1,825 days. In sensitivity analyses, 2-year partial prevalence will be estimated (using records in the prior 730 days) as will complete prevalence. For the latter, individuals will continue to be considered as a prevalent case from their first observed diagnosis or observation of acute lymphocytic leukaemia up until the end of their observation time.

	D2.2.3 – Study Protocol for C1-001	
	Author(s): [name], [name], [name], [name]	Version: 2.0 - Final
	Dissemination level: Public	

Table 4. Operational definition of the different outcomes

Outcome name	Details	Primary outcome?	Type of outcome	Wash out window	Care Settings ¹	Code Type ²	Diagnosis Position ³	Applied to study populations:	Measurement characteristics/ validation	Source of algorithm
Follicular lymphoma	For clinical description of outcome, see above	Yes	Binary	N/A	Primary care and combination of primary and secondary care for IQVIA Germany	SNOMED	N/A	All individuals within the selected databases	N/A	N/A
Diffuse Large B-Cell Lymphoma	For clinical description of outcome, see above	Yes	Binary	N/A	Primary care and combination of primary and secondary care for IQVIA Germany	SNOMED	N/A	All individuals within the selected databases	N/A	N/A
Multiple myeloma	For clinical description of outcome, see above	Yes	Binary	N/A	Primary care and combination of primary and secondary care for IQVIA Germany	SNOMED	N/A	All individuals within the selected databases	N/A	N/A
Chronic lymphoc	For clinical	Yes	Binary	N/A	Primary care and	SNOMED	N/A	All individuals	N/A	N/A

	D2.2.3 – Study Protocol for C1-001	
	Author(s): [name], [name], [name], [name]	Version: 2.0 - Final
	Dissemination level: Public	

Outcome name	Details	Primary outcome?	Type of outcome	Wash out window	Care Settings ¹	Code Type ²	Diagnosis Position ³	Applied to study populations:	Measurement characteristics/ validation	Source of algorithm
lytic leukaemia	description of outcome, see above				combination of primary and secondary care for IQVIA Germany			all within the selected databases		
Acute myeloid leukaemia	For clinical description of outcome, see above	Yes	Binary	N/A	Primary care and combination of primary and secondary care for IQVIA Germany	SNOMED	N/A	All individuals within the selected databases	N/A	N/A
Acute lymphocytic leukaemia	For clinical description of outcome, see above	Yes	Binary	N/A	Primary care and combination of primary and secondary care for IQVIA Germany	SNOMED	N/A	All individuals within the selected databases	N/A	N/A

N/A: not applicable for this study or data sources being used

	D2.2.3 – Study Protocol for C1-001	
	Author(s): [name], [name], [name], [name]	Version: 2.0 - Final
		Dissemination level: Public

8.6.3. Other covariates, including confounders, effect modifiers and other variables (where relevant)

Two age groupings will be used: 1) 0-9; 10-19; 20-29; 30-39; 40-49; 50-59; 60-69; 70-79; 80-89; 90-99; 100+, and 2) 0-44; 45-64; 65 and over. The latter, broader, age groups will be used where low counts preclude reporting results for the 10-year age bands. The sex (male/ female) of study participants will also be identified.

